Control: This is a pilot proof of concept study with sample size insufficient for a formal randomized comparison. In order to have a valid comparator, participants will be randomly allocated to an intervention and control group (approx. 40 per group). No p values will be calculated. Comparisons will be as risk ratios or mean differences with 95% confidence intervals.

Outcomes

Baseline demography and clinical data will be recorded.

Primary: The primary outcome is the combined frequency of adverse device effects and device deficiencies up to discharge from hospital.

Adverse device effects (ADEs) encompass any adverse event with a reasonable causal relationship resulting from insufficient or inadequate instructions for use; problems with the deployment, implantation, installation, or operation of the device; malfunction of the device; or user error or intentional misuse of the device. They will include device deficiencies such as device expulsion / falling out of the uterus, failed maintenance of suction pressure and tube blockage.

A Serious Adverse Device Effect (SADE) is an adverse device effect that has resulted in any of the consequences characteristic of a serious adverse event. An example of this would be the need for further intervention to treat trauma caused by the device (e.g. sutures, laparotomy, etc).

Secondary efficacy outcomes will include:

- 1. Measured blood loss within 30 minutes after insertion (ml)
- 2. Blood loss >500ml
- 3. Blood loss >1000ml
- 4. Efficiency of suction (assessed through ultrasound assessment of residual blood in the uterus at 30 minutes or blood expressed from the uterus after tube removal)
- 5. Blood pressure, pulse and shock index 15 minutes after vaginal birth or caesarean
- 6. Change in routinely collected haemoglobin levels pre delivery to post delivery
- 7. Blood transfusion
- 8. ICU admission
- 9. Death
- 10. Functionality and acceptability:
 - a. Active bleeding from the uterus continuing for more than 10 minutes (main efficacy outcome).
 - b. Any adverse event
 - c. Pain experienced (No pain/Mild /Severe/Unbearable)
 - d. Need for Additional interventions to stop bleeding (e.g. more uterotonics, compressive measures, UBT, laparotomy, hysterectomy)
 - e. Was STUT effectively inserted? (Yes/No/Unknown)
 - f. How easy was it for health care providers to insert the Suction Tube Uterine Tamponade (easy/moderately difficult/Difficult/failed)

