- g. Did the suction tube remain in place in the uterus until removal (Yes/No/Unknown)
- h. Did the suction tube establish a good seal (no loss of suction) (Yes/No/Unknown)
- Did the suction tube interfere with or facilitate examination for and management of lower genital tract bleeding after vaginal birth (Facilitated/Interfered/Neither/not applicable/Unknown)
- j. Did the suction tube interfere with or facilitate surgical exposure during caesarean birth (Facilitated/Interfered/Neither/Unknown)
- k. Was there any blockage of the suction tube (Yes/No/Unknown)

Recruitment and consent

We plan to approach women at increased risk of PPH awaiting caesarean or induction of labour, pre-labour or in early labour and provide written and/or video information to them. They will be given time to discuss participation with friends and family and then invited to provide signed consent. Consent will be confirmed verbally immediately after birth, prior to device insertion.

Sample size

We aim to use the U-STAT in 40 participants, with a minimum of 25% being vaginal births and 25% caesarean section. 35 participants will provide 90% confidence that the true rate of adverse device effects and device deficiencies is under 10% (+/-10%). The sample is increased to 40 to account for any unexpected procedural difficulties in the first 5 recruits.

Procedures

Participating sites will be supplied with a 'PPH emergency trolley' containing all the supplies needed for STUT and emergency treatment of PPH, as well as forms for screening, enrolment, randomization and data collection. After vaginal birth, the suction tube will be inserted under sterile conditions transvaginally into the uterine cavity. Suction will be applied either with the manual suction device or with a surgical suction unit, set at 100mmHg suction pressure. If there is excessive bleeding which is not controlled by the STUT, the suction tube will be removed and management continued according to local protocols. If effective, the STUT suction will be interrupted every 30 minutes, and removed as soon as bleeding is controlled without suction. All other care will follow local practice. Blood loss will be measured from enrolment until bleeding is controlled (minimum 30 minutes), using a blood collection drape or Maternawell tray, plus blood collected in the UVT suction bottle, surgical suction and swabs.

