19. Tamponade device inserted? 2=Other tube*; 3=Ellavi; 4 = Other	· ·				
20. Time device inserted:		:			

21. Ease of insertion? 1=easy, 2=mod.diff, 3=difficult		
22. Device stable in uterus? 0=No; 1=Yes		
23. Tube air leak? 0=No; 1=Yes; 3=No tube		
25. Effect of device on exam/mx? 1. Facilitated, 2. Interfered, 3.Neither		
26. Exam obscured by blood from ut: 0=No; 1=Yes		
27. Time bleeding stopped.	:	
28. Time vital signs check (+ 15min)	:	
29. Syst BP mmHg		
30. Diast BP mmHg		
31. Pulse /m		
32. Additional oxytocin 0 = No 1= Yes		
33. Additional erg-/syntomentrine 0 = No 1= Yes		
34. Additional misoprostol 0 = No 1= Yes		
35. Additional tranexamic acid 0 = No 1= Yes		
36. Time blood collection measured (>30 min)	:	
37. Blood volume excluding suction jar (ml)		
38. Blood volume in suction jar (ml)		
39. Blood expelled ex ut. after removal of device or after 30 min in control group (ml)		
40. If bleeding persists, measured blood loss post 30min		
41. Laparotomy 0 = No 1= Yes		
42. Compression sutures 0 = No 1= Yes		
43. Uterine devascularization 0 = No 1= Yes		
44. Hysterectomy 0 = No 1= Yes		
45. Other procedure 0 = No 1= Yes*		
46.ICU admission 0 = No 1= Yes		
47. Organ failure 0 = No 1= Yes*		

48. Death 0 = No 1= Yes		
49. Blood transfusion (number of units RBCs)		
50. First Haemoglobin after bleeding controlled (g/dL)		
51. Highest temperature (deg C)		
52. Endometritis 0 = No 1= Yes 9=Unknown		
53. Other complications 0 = No 1= Yes* 9=Unknown		
53. Date of Discharge (DD/MMM/YY)	/ /	

Completed by (initials) :	Date completed	(dd/mmm/yy)
Completed by (initials) .	Date completed	(dd/IIIIIII/yy

Vaginal birth Clinical checklist (remains in hospital records)

Equity for Suction Tamponade Access to treat postpartum haemorrhage: The ESTA project

	1.	○ Consent signed
	2.	Confirm with Mother that still happy with consent
	3.	Ostudy trolley is available with register, U-STAT suction tubes, working suction
	4.	Clean drape or Maternawell tray available
	5.	\bigcirc Manual suction device ready with vacuum pumped or suction machine pressure set to 100mmHg – block tubing to check
	6.	After baby born position drape/Maternawell tray below the buttocks
Aft	er p	lacenta delivered completely:
	7.	Examine vaginally to exclude major lower genital tract trauma
	8.	O Note the time, 24 hr: H H : M M
	9.	○ Open next numbered envelope and note allocation: ○ STUT* ○ Control
	10.	*Insert U-STAT tube to fundus of uterus and start suction

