	11.	\bigcirc *Insertion of tube; \bigcirc easy, \bigcirc moderately difficult, \bigcirc difficult, \bigcirc Failed, \bigcirc not done
	12.	Alternative Management
	13.	*Time tube insertion procedure completed 24 hr: H H : M M
	14.	*Check tube/balloon stable in uterus Yes / No / Onot used
	15.	Ocontinue routine care including repair of bleeding tears
	16.	*Effect of device on exam/mx of lower genital tract bleeding? Facilitated; Interfered; Neither; Unknown
	17.	○ Note the time per vaginal bleeding stopped. 24 hr: H H : M M
	18.	○ 15 minutes after insertion (10 above) note time 24 hr: H H : M M
		Systolic BP Diastolic Pulse
	19.	○ 30 minutes after insertion, note time. 24 hr: H H : M M
	20.	
		ml ml
	21.	Replace empty tray, expel blood from the uterus by fundal massage (into tray)
	22.	○ Measure blood loss in tray = RESIDUAL
		ml ml
	23.	*disconnect suction. If no bleeding in 10 minutes, remove U=STAT tube
	2/	*If bleeding continues replace empty tray continue suction plus other measure

25. When bleeding stopped, measure blood loss in tray = Secondary blood loss
ml ml
26. *Measure blood loss in suction bottle
ml ml
27.
○ None
The participants will be followed till discharge and the outcome data, as well as any complications, recorded.

Caesarean birth Clinical checklist (remains in hospital records)

Equity for Suction Tamponade Access to treat postpartum haemorrhage: The ESTA project

	1.	○ Consent signed
	2.	Oconfirm with Mother that still happy with consent
	3.	OStudy trolley is available with register, U-STAT suction tubes, working suction
	4.	Clean drape or Maternawell tray available for post-op use
	5.	○ Manual suction device ready with vacuum pumped or suction machine pressure set to 100mmHg – block tubing to check
	6.	\bigcirc After birth of baby, open next numbered envelope and note allocation: \bigcirc STUT* \bigcirc Control
Aft	er p	placenta delivered completely:
	7.	○ Note the time, 24 hr: H H : M M
	8.	\bigcirc *Insert U-STAT tube to fundus of uterus and lower end through cervix and vagina, ask assistant to connect and start suction
	9.	\bigcirc *Insertion of tube; \bigcirc easy, \bigcirc moderately difficult, \bigcirc difficult, \bigcirc Failed, \bigcirc not done
	10.	. Alternative Management
	11.	. *Time tube insertion procedure completed 24 hr: H H : M M
	12.	. Continue uterine closure
	13.	*Effect of device on visualisation for uterine closure? \(\text{Facilitated}; \text{Interfered}; \) Neither; \(\text{Unknown}\)

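### No visible form item reads the device suction bottle at 30 minutes, so in women kept on suction later bottle blood cannot be separated from the 30-minute blood-loss outcome

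*Protocol*

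**What the plan says.** Outcomes, secondary efficacy outcome 1, is "Measured blood loss within 30 minutes after insertion (ml"). Procedures sets a different window: "Blood loss will be measured from enrolment until bleeding is controlled (minimum 30 minutes"), with the total made up of the drape or tray "plus blood collected in the UVT suction bottle, surgical suction and swabs".

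The Vaginal birth Clinical checklist marks device-arm steps with an asterisk. Its relevant steps are:

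- Item 19, both arms: "30 minutes after insertion, note time".
- Items 21–22, both arms: an empty tray is put in place, the uterus is massaged, and the blood expelled is recorded as residual.
- Item 23, device arm: "disconnect suction. If no bleeding in 10 minutes, remove U=STAT tube".
- Item 24, device arm: "If bleeding continues replace empty tray continue suction plus other measure".
- Item 25, both arms: tray loss after that point is recorded separately once bleeding has stopped.
- Item 26, device arm: "Measure blood loss in suction bottle".

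The Caesarean birth Clinical checklist takes a bottle reading at uterine closure (item 15). It reads the drape or tray at 30 minutes from placental delivery (items 21–22) and the residual after that (item 23). Suction is then disconnected, with reconnection if bleeding resumes (item 24), and the bottle is read again at item 25.

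The ESTA Study Clinical Record Form has one jar field, "Blood volume in suction jar (ml") at item 38. It has one collection time, later than 30 minutes (item 36), and a field for loss after 30 minutes if bleeding persists (item 40).

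**The concern.** A 30-minute outcome needs every component of the loss to be cut at 30 minutes. The tray is cut there; the device bottle, on the visible text, is not. The bottle is where the device sends uterine blood, so the component without a cut belongs to the device arm. Continued suction is also foreseen: the Intervention paragraph keeps suction on if bleeding resumes, and Procedures has it interrupted at 30-minute intervals.

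The trial is meant to give an indication of effectiveness ahead of a larger trial, through mean differences with 95% confidence intervals. A one-sided recording error in a blood-loss outcome weakens that purpose, and a bottle level that nobody recorded at 30 minutes cannot be recovered in the analysis. The outcomes of loss above 500 ml and above 1000 ml state no time window. They would inherit the error only if they are built from the 30-minute total.

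**Working it through.** The Protocol gives no figure that depends on this point, so there is nothing to reproduce. The check is to trace each volume by time and arm, then gauge the scale.

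**Trace of the volumes**

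| Component | Split at 30 minutes? | Where |
|---|---|---|
| Tray, vaginal, both arms | Yes | Tray changed after item 19; residual at 22; later loss at 25 |
| Drape or tray, caesarean, both arms | Yes | Read at items 21–22; residual at 23 |
| Device bottle, vaginal | No visible reading | Only item 26, after items 23–25 |
| Device bottle, caesarean | No visible reading | Item 25, after possible reconnection; item 15 is at uterine closure |
| CRF jar volume | No | Single item 38, with the single time at item 36 |
| CRF loss after 30 minutes | Field exists | Item 40; does not say whether tray, jar or both |

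Two cases follow for a device-arm woman.

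1. Bleeding does not resume. Suction is disconnected directly after the 30-minute steps, so the final bottle volume is close to the 30-minute volume and the excess is near zero.
2. Suction is continued or reconnected. All later bottle blood joins the single jar figure, and no earlier reading allows it to be subtracted.

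A smaller effect may apply outside case 2. Massage (vaginal item 21, caesarean item 23) comes before disconnection (items 23 and 24), so some residual blood may pass into the bottle instead of the tray. CRF item 39 times the residual in the device arm at removal of the device, which does not match that order. The Protocol gives no basis for sizing this.

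**Scale**

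Shift in the device-arm mean = f × v, where f is the share of device women with suction past 30 minutes and v is their late bottle volume. Neither is in the Protocol; both are assumed.

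- Low: 0.05 × 50 = 2.5 ml
- Middle: 0.10 × 150 = 15 ml
- High: 0.20 × 300 = 60 ml

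With 40 women in the arm, f of 5–20% is 2 to 8 women.

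For comparison, the 95% half-width of a mean difference with 40 per arm is 1.96 × SD × √(2/40):

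- SD 496 ml (Background, loss at caesarean birth): 1.96 × 496 × 0.2236 ≈ 217 ml
- SD 300 ml (assumed): ≈ 132 ml
- SD 200 ml (assumed): ≈ 88 ml

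The high-end shift of 60 ml is about 28% of the half-width at SD 496 ml (60/217) and about 68% at SD 200 ml (60/88).

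**The case against.** The strongest reply has four parts.

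**The forms hold more than a single bottle reading and a 30-minute stop for controls.** This stands. A reader might infer that there is only one bottle reading anywhere, and that control loss ends at 30 minutes while device loss is open-ended. The caesarean checklist has an earlier reading at item 15, although uterine closure is not the 30-minute point. Vaginal item 25 and CRF item 40 apply to both arms, so later control loss is recorded, but separately. At caesarean the surgical estimate (item 18) is timed to skin closure in both arms. The difference between arms is that tray loss can be split at 30 minutes and bottle loss visibly cannot.

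**Item 40 and unseen documents may cover it.** The Protocol promises data-entry guidelines and an analysis plan fixed before recruitment, and either could say how items 37–40 combine. They could settle the arithmetic. Without a 30-minute bottle reading, though, there is no volume for them to use.

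**The wording of item 20 cannot be read in either checklist in the text at hand.** Vaginal item 20 has a volume box right after the 30-minute time and leads into a tray change. A tray reading is most likely, but a bottle reading cannot be excluded. Caesarean item 20 comes before the 30-minute time is noted, and the visible 30-minute reading there is of the drape or tray. The CRF text is intact and offers one jar field in any case.

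**The effect is small and not on the main outcome.** This stands in part. The primary outcome is device effects and deficiencies, the main efficacy outcome is 10a (continued active bleeding), no p values are planned, and the assumed shift is below the confidence half-width. A reader might also infer that massage adds blood to the bottle in every device woman. The vaginal form directs expelled blood into the tray and both forms record it as residual, so only possible leakage can be claimed.

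**Conclusion.** The point holds in a limited form. On the visible text, the 30-minute outcome cannot be measured as defined in device-arm women whose suction is continued or reconnected, because bottle blood before and after 30 minutes ends up in one figure. The end-of-suction reading suits the window in Procedures but not the one in outcome 1.

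The direction is against the device. The size is unknown: about 2.5–60 ml on the device-arm mean, resting wholly on the assumed 5–20% and 50–300 ml. In women whose suction stops after the 30-minute steps the excess is near zero, apart from any massage blood entering the tube. The conclusion also assumes that vaginal item 20 is a tray reading; if it included the bottle, the gap at vaginal birth would narrow to the missing CRF field. It is a modest data-capture defect, worth correcting before recruitment because it cannot be corrected afterwards.

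**What to change.** 1. On both checklists, record the bottle level at the 30-minute point together with the tray or drape and before massage, and keep the existing reading at the end.
2. Split CRF item 38 into 38a (jar at 30 minutes) and 38b (jar at end).
3. Define item 40 as post-30-minute tray loss plus (38b − 38a), so that late bottle blood is counted once.
4. Build outcome 1 from the 30-minute tray or drape reading, 38a and the other 30-minute components. At caesarean, say how the reading at uterine closure and the surgical estimate enter. Use 38b only for total loss.
5. Give outcome 1 one time origin that exists in both arms. Controls have no insertion, and the caesarean form already counts from placental delivery. The time noted in both arms at vaginal item 8 and caesarean item 7 is a candidate.

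The cost is one extra reading of a bottle already in use, one more CRF field, and short wording changes to item 40 and outcome 1. Sample size and randomisation are unaffected.

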This application is an investigator-initiated, University-sponsored academic research program. Sinapi Biomedical are sub-contracted to supply the device. Sinapi manufactures a CE marked Ellavi balloon uterine tamponade system (Fig 1). The central tube is very similar to the Levin tube, but without the multiple suction holes, and served as the starting point for development of the U-STAT device.

Methods

This exploratory proof of concept (POC) clinical trial will build on our experience with our initial clinical studies of the improvised STUT device. This initial trial is designed to assess essential safety, performance, feasibility and acceptability and to give an indication of effectiveness and suitability for a substantive randomized effectiveness trial. It will include a limited number of participants (intervention arm n=40, control arm n=40).

Study type: Investigator-initiated, academic, non-commercial study.

Study Sponsor. Wits Health Consortium, a subsidiary of University of the

Witwatersrand

Study Design: Prospective intervention study

Study Sites: Frere/Cecilia Makiwane hospitals, South Africa

Study Duration: Four months

Study Population: Women 18 years old or more with risk factor(s) for PPH, for planned vaginal or caesarean birth; no serious medical conditions.

Inclusion Criteria

- Age 18 years and older
- Planned vaginal or caesarean birth
- One or more risk factors for PPH. These include
 - o Previous PPH
 - o Hypertension and pre-eclampsia
 - o Induction of labour
 - o Emergency caesarean birth
 - O Anaemia
 - Multiple pregnancy
 - Polyhdramnios
 - Macrosomia
 - Antepartum haemorrhage
- No serious medical conditions
- Provision of signed written informed consent

Intervention: Suction Tube Uterine Tamponade (STUT) using the purpose-designed soft plastic suction catheter inserted after vaginal birth or during caesarean birth. Low-pressure suction applied (approx. 100mmHg). Suction stopped after 30 minutes. If no further bleeding, tube removed. If bleeding resumes, suction continued. If bleeding not controlled within 20 min (or sooner if clinically indicated), proceed to further management according to local standard of care protocols (these might include additional uterotonics, tranexamic acid, compression methods, uterine balloon tamponade or laparotomy).

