Enrolment will take place immediately after birth of the baby when the participant's name is entered in the enrolment register and allocation takes place by opening the next in a consecutively numbered series of opaque sealed envelopes with allocation cards in computer-generated random sequence in balanced blocks of variable size, stratified by mode of birth. Participants will remain in the trial whether or not the intervention is applied, on the 'intention to treat' principle. Good Clinical Practice (GCP) procedures will be followed.

A clinical checklist will be completed by the attending clinician, which will form part of the patient clinical record. Data will be entered onto paper or electronic CRFs by the research staff.

Quality control will be performed on-site: the research staff will be responsible for ensuring that the CRFs are correctly filled out. Completed CRFs will be checked against the original patient records for correct completion. Any discrepancies will be immediately addressed.

Data management

Because of the small number of participants and limited data per participant, complex data entry strategies will not be needed. Data will be entered onto paper or electronic CRF's, checked for accuracy at source, and stored in a locked filing cabinet or password-protected computer. The data will be entered onto an excel spreadsheet and analysed using Epi Info software.

Adverse events and serious adverse events, whether thought to be related to the trial intervention or not, will be recorded by the site PIs on standard adverse events forms which will be submitted to the University ethics committee and DSMC.

Data protection procedures

The following measures will be taken to ensure participant confidentiality:

- Trial data sets for each participant will be identified by a unique ID number, not the participant's name
- The trial register of names and trial ID numbers, and consent forms will be kept separate from the CRFs
- Trial documents will be kept securely under lock and key and will not be accessible, other than to the research teams
- Data will be entered by trial ID number onto a password-protected database to which only trial staff will have access
- The trial report will not contain the names of any participants
- After completion of the trial, the trial documents will be kept under lock and key for five years

Personal information

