The clinical trial will include use of personal demographic and clinical information of participants. The information will be de-identified using a trial ID number and stored in a password-protected computer. Paper trial documents will be stored under lock and key.

Data analysis

Data management will be conducted by the Liverpool University Clinical Trials Unit. The locked database will then be passed to the investigators for analysis.

For continuous variables, the number of participants, number of missing values, minima, maxima, means and standard deviations will be reported, with 95% confidence intervals. If distribution is not normal, medians and interquartile range (IQR) will be reported.

For categorical variables, the number of participants, number of missing values and percentages will be reported, with 95% confidence intervals.

Comparisons will be expressed as risk ratios or mean differences with 95% confidence intervals. As the study is not powered for statistical analysis, no p values will be reported.

Data sharing and access

Data will be made available after publication of results on reasonable request based on an ethically approved research protocol. Data sharing is included in the participant information.

Trial registration

The protocol will be registered with SANCTR and ISRCTN.

Research team

[name] is a senior researcher with expertise in clinical trials. **[name]** is a researcher with many years' experience conducting non-regulatory and regulatory clinical trials

The Trial Management Group will be responsible for governance and oversight. [name] will be overall responsible for the clinical trial conduct, whilst [name] will supervise the clinical trial.

Facilities

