	14.	. Time uterus closed 24 hr: H H : M M
	15.	. Measure blood volume in suction bottle = pre-suction volume:
		ml ml
	16.	*Note the time bleeding through suction tube stopped. 24 hr: H H : M M
	17.	. O 15 minutes after placental delivery (7 above) note time 24 hr: H H : M M
		Systolic BP Diastolic Pulse
	18.	. After skin closure, estimate surgical blood loss (excluding U=STAT tube drainage)
		ml ml
	19.	. O In recovery room: Place drape or Maternawell tray under participant's buttocks
	20.	
	21.	. O 30 minutes after placental delivery (7 above), note time. 24 hr: H H : M M
	22.	. Swab vagina and measure blood loss in drape/tray = postop blood blood

23. O Place new tray or drape under participant and express blood from uterus -
Measure blood loss in drape/tray = RESIDUAL blood
ml ml
24. *Disconnect suction, if no bleeding after 10 minutes, remove U-STAT tube. If
bleeding resumes, reconnect suction and manage as per hospital protocol
25. *Measure blood loss in suction bottle
ml ml
26. *Suction tube problems: Fell out; blocked; leaking; Poor suction
○ None

ml

The participants will be followed till discharge and the outcome data, as well as any complications, recorded.

Participant questionnaire (Vaginal birth Intervention group only)

Protocol Title: Equity for Suction Tamponade Access to treat postpartum haemorrhage: The ESTA project			
Site Number:	Subject ID:	Date:(dd/mmm/yy)	
Dear Participant, thank you for assisting us with the ESTA project. Pease would you answer the following questions. There are no right or wrong answers. Please just give us your personal opinions. Please feel free not to answer if you prefer not to.			
Questionnaire		Comment/Notes	
*After the hirth of your ba	by a tubo was	T	
*After the birth of your baby, a tube was inserted to your uterus to help reduce bleeding Please could you describe the pain you experienced? 0=No pain; 1 = Mild pain; 2 = Severe pain; 3 = Unbearable pain; 4 = unsure; 9 = no data			
*Please could you describe when the tube was removed = Mild pain; 2 = Severe pain Unbearable pain; 4 = unsure	d? 0=No pain; 1 u; 3 =		
*Please could you describe overall about the suction tub 0= fine; 1 = uncomfortable b = Unacceptable; 3 = Unbear unsure; 9 = no data	pe procedure? out acceptable; 2		
Thank you for assisting with this questionnaire			

Date completed

(dd/mmm/yy)

Completed by (initials):

Participant questionnaire (Caesarean birth Intervention group only)

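### The main efficacy outcome (10a, uterine bleeding beyond 10 minutes) is not ascertained like-for-like between arms: at caesarean the only legible bleeding-stopped line fits the device arm alone, and at vaginal birth the line can miss blood leaving by the tube

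*Protocol*

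**What the plan says.** Outcome 10a in the Protocol's Outcomes section is "Active bleeding from the uterus continuing for more than 10 minutes (main efficacy outcome"; no start is given for the 10 minutes. The Data analysis section says "Comparisons will be expressed as risk ratios or mean differences with 95% confidence intervals", so this binary outcome becomes a risk ratio. The arms are "intervention arm n=40, control arm n=40", the device arm is recruited "with a minimum of 25% being vaginal births and 25% caesarean section", and allocation is "stratified by mode of birth".

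Three forms bear on the outcome:

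- **Caesarean checklist, item 16:** "Note the time bleeding through suction tube stopped". The line carries an asterisk.
- **Vaginal checklist, item 17:** "Note the time per vaginal bleeding stopped". The line carries no asterisk.
- **Clinical Record Form:** "27. Time bleeding stopped". The field is limited neither to an arm nor to a mode of birth.

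On both checklists the allocation line puts an asterisk on STUT and none on Control, and the starred steps concern the tube. The section on conduct during recruitment makes the checklist part of the clinical record and has record forms checked against patient records.

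**The concern.** Outcome 10a can be derived only from a time at which bleeding stopped. On the forms that time means flow through the tube (caesarean, device), nothing legible (caesarean, control) or visible vaginal flow (vaginal birth, both arms). The outcome itself is bleeding from the uterus, and in the device arm uterine blood has two exits.

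The Methods section wants the trial to indicate effectiveness and suitability for a larger randomised trial, and 10a is the efficacy outcome it singles out. Leaving out p values does not protect a risk ratio from unequal measurement, and no later analysis can recover a time that nobody noted.

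**Working it through.** The plan gives no figure for this outcome, so there is none to reproduce. The check compares the forms, then shows the scale with assumed risks.

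**1. Sources for record form item 27**

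| | Device arm | Control arm |
|---|---|---|
| Vaginal birth | Item 17: vaginal flow | Item 17: vaginal flow |
| Caesarean | Item 16: tube flow | No legible line |

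The caesarean gap does not depend on the asterisk: a line about tube flow cannot apply where there is no tube. In the vaginal checklist, item 26 (starred) measures blood in the suction bottle, but no legible line times the end of tube flow.

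**2. Start of the clock**

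Outcome 10a states none, and the checklists do not supply a common one. The 15-minute vital signs are timed from tube insertion at vaginal birth (item 18) and from placental delivery at caesarean (item 17). Insertion has no meaning for a control.

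**3. How many controls are affected**

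With at least 25% of each mode, caesareans are 25% to 75% of the device arm: 0.25 × 40 = 10 to 0.75 × 40 = 30. Balanced blocks stratified by mode make the control figure about the same.

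**4. Vaginal births (illustration)**

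Assume equal true risk p in both arms. Let m be the fraction of device-arm women still bleeding through the tube at 10 minutes who are timed as stopped.

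Observed RR = p(1 − m)/p = 1 − m

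This gives 0.90, 0.75 and 0.50 for m = 0.10, 0.25 and 0.50. The documents do not give m; it is 0 if staff also watch the tube.

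**5. Pooled modes, caesarean control times missing (illustration)**

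Let s be the caesarean share and p_v, p_c the assumed risks by mode, with true RR 1. Device-arm caesareans are kept.

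Observed RR = [(1 − s)p_v + s·p_c]/p_v

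| s | p_v 10%, p_c 20% | both 20% | p_v 20%, p_c 10% |
|---|---|---|---|
| 0.25 | 1.25 | 1.00 | 0.875 |
| 0.50 | 1.50 | 1.00 | 0.75 |
| 0.75 | 1.75 | 1.00 | 0.625 |

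The error can go either way, depending on how risk differs by mode.

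**6. Precision if only vaginal births are compared**

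Assume 20% risk in both arms and n vaginal births per arm.

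SE(log RR) = √[2(1 − p)/(np)]; 95% CI around RR 1 = exp(±1.96·SE)

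- n = 10: 0.17 to 5.77
- n = 20: 0.29 to 3.45
- n = 30: 0.36 to 2.75
- n = 40 (all births, for comparison): 0.42 to 2.40

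**The case against.** A reader might infer that the outcome has no source at all for caesarean controls and that its risk ratio cannot be estimated. The documents do not support that. Item 27 is open to every participant, and item 39 of the same form names the control group, so research staff can enter a time for a caesarean control. Caesarean item 20 has lost its text, so the absence of a control line cannot be asserted. These objections stand, and they limit the claim to a missing common definition and no legible checklist source. Item 20 would be unlikely to cure the asymmetry: it follows the 15-minute check, skin closure and placement of the recovery-room tray, which is late for a 10-minute threshold and a different route from item 16.

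A reader might also infer a demonstrated bias towards the device in vaginal births. That goes too far. Both arms use the same line, nothing tells staff to ignore the tube, and only a woman bleeding through the tube without visible vaginal loss would be misclassified. An opposite error is possible: blood may collect in a control's uterus with little visible loss, and the protocol measures such residual blood. The net direction is not established.

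That the asterisk means device arm only is inferred, not stated. Finally, 10a is a secondary outcome in an exploratory study without p values, and blood loss is also measured by tray or drape, suction and swabs. That lowers the severity but does not make 10a comparable.

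**Conclusion.** The point holds in limited form, at moderate severity. Completed as written, the forms give times for the main efficacy outcome that are not comparable between arms. At caesarean, about 10 to 30 of 40 controls have no legible checklist line or definition behind item 27, while device-arm women are timed on tube flow. At vaginal birth the shared line can miss tube flow, which could favour the device by an amount the documents do not allow one to estimate.

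This rests on the natural reading of the asterisk, on the lost caesarean item 20 not being an arm-neutral stop time, and on roughly equal caesarean shares in the two arms. The risk ratios above are illustrations, not predictions. The primary outcome, device effects and deficiencies, is untouched.

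**What to change.** Define 10a and record form item 27 once, for both arms and both modes: the time when no active uterine bleeding is seen by any route (vagina or tube), counted from placental delivery. Both checklists can time that start, at caesarean item 7 and vaginal item 8; the latter follows the vaginal examination, so it should say that the time is that of placental delivery.

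Reword vaginal item 17 to this definition, including tube flow in the device arm. Replace caesarean item 16 with an unstarred line that can be completed in both arms.

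Whether the time can be observed in caesarean controls needs testing, because the tray is placed only in the recovery room. The pilot of procedures and forms already planned before recruitment is the place to do it. If it cannot be observed, report the 10a comparison for vaginal births only and say so. The price is precision: 10 to 30 per arm instead of 40, with the wider intervals shown above.

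Otherwise the cost is two reworded checklist lines, one clarified label and a brief look at the tube or bottle. Clinical care does not change.
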